2.4.4.5.2 Analysis of systemic corticosteroid (SCS)

SCS exposure in the dupilumab versus placebo exposed groups will be evaluated by total SCS intake in days, number of courses of SCS, and time to first SCS use. This will be evaluated in the population with the Type 2 inflammatory asthma phenotype and the population with baseline blood eosinophils ≥ 0.3 Giga/L. Total SCS intake in days, and number of courses during the treatment period, will be summarized by treatment groups of Dupilumab and placebo with the treatment duration defined as in [Section 2.4.4.1](#). A course of SCS is considered continuous if treatment is separated by less than 7 days.

For patients who discontinue treatment, data collected during the off- treatment period will also be used.

Descriptive statistics including number of subjects, mean, standard deviation, min, and max will be provided together with annualized number of courses or annualized total dose. The annualized number of courses of SCS intake during the treatment period will be analyzed using a negative binomial regression model. The model will include the number of courses of SCS intake during the treatment period as the response variable, and same set of covariates as defined in [Section 2.4.4.1](#).

Time to the first use of SCS during the 52-week placebo-controlled treatment period will be analyzed as time to event variable using same method as stated in [Section 2.4.4.3.2](#) in both the Type 2 inflammatory asthma phenotype and baseline blood eosinophils ≥ 0.3 Giga/L population.

2.4.4.5.3 Annualized rate of Loss of asthma control (LOAC)

If a patient stays in the study until the end of the 52-week treatment period, all LOAC events that happen up to Week 52 visit will be included in the analysis, regardless whether the patient is on-treatment or not, and the observation duration is defined as from randomization to Week 52 visit. If a patient withdraws from the study prior to the end of the 52-week treatment period, all observed LOAC events up to the last contact date will be included in the analysis, and the observation duration is defined as from randomization to the last contact date. Patients who prematurely discontinue treatment will have off-treatment measurements included in the analysis up to either Week 52 or study withdrawal, whichever comes earlier.

The annualized rate of LOAC events will be analyzed using negative binomial regression model in the Type 2 inflammatory asthma phenotype and baseline blood eosinophils ≥ 0.3 Giga/L populations. This model includes the total number of events that occur during the observation period defined above as the response variable, with the treatment arm, age, baseline weight (≤ 30 kg, > 30 kg), region, baseline eosinophil level (< 0.3 Giga/L, ≥ 0.3 Giga/L), baseline FeNO level (< 20 ppb, ≥ 20 ppb), baseline ICS dose level (medium/high) and number of severe exacerbation events within 1 year prior to the study as covariates. When performing the analysis in the baseline blood eosinophils ≥ 0.3 Giga/L population, the baseline eosinophil level will be removed from the model covariates.

2.4.5 Analyses of safety data

The summary of safety results will be presented by treatment group actually received.

General common rules

All safety analyses will be performed on the safety population as defined in [Section 2.3.2](#).

- Analysis of TEAE as defined in [Section 2.4.5.1](#)
 - Analysis of all treatment-emergent adverse events
 - Analysis of all treatment-emergent serious adverse event(s)
 - Analysis of all treatment-emergent adverse event(s) leading to permanent treatment discontinuation or drug interruption
 - Analysis of adverse events of special interest (AESI) and other selected AE groupings
 - Death
- Change in blood eosinophil as defined in [Section 2.4.5.3](#)

Unless otherwise specified, following common rules will be applied:

- The baseline value is defined as the last available value before the first dose of IMP
- The potentially clinically significant abnormality (PCSA) values are defined as abnormal values considered medically important by the Sponsor according to predefined criteria/thresholds based on literature review and defined by the Sponsor for clinical laboratory tests, vital signs, and ECG for this age group (PCSA version dated May 2014 [[Appendix A](#)])
- PCSA criteria will determine which patients had at least 1 PCSA during the treatment-emergent adverse event period, taking into account all evaluations performed during the treatment-emergent adverse event period, including nonscheduled or repeated evaluations. The number of all such patients will be the numerator for the on-treatment PCSA percentage
- The treatment-emergent PCSA denominator by group for a given parameter will be based on the number of patients assessed for that given parameter in the treatment-emergent adverse event period by treatment group on the safety population. Number (%) of patients

with at least 1 PCSA will be summarized regardless of baseline PCSA status and also by baseline PCSA status

- For quantitative safety parameters based on central laboratory/reading measurements, descriptive statistics will be used to summarize results and change from baseline values by visit and treatment group. Summaries will include the endpoint value and/or the worst on-treatment value. The endpoint value is commonly defined as the value collected at the end of treatment. If this value is missing, this endpoint value will be the closest value prior to the end of treatment epoch. The worst value is defined as the nadir and /or the peak post-baseline (up to the end of treatment epoch or EOT) according to the direction (minimum or maximum) of the abnormality as defined in the PCSA list
- The analysis of the safety variables will be essentially descriptive and no systematic testing is planned
- All safety values including unscheduled measurements will be assigned to the appropriate safety analysis visit window defined in [Section 2.5.4](#)

2.4.5.1 Analyses of adverse events

General information

The primary focus of adverse event reporting will be on treatment-emergent adverse events. Pretreatment adverse events will be described separately.

If an adverse event date/time of onset (occurrence, worsening, or becoming serious) is incomplete, an imputation algorithm will be used to classify the adverse event as pretreatment or treatment-emergent. The algorithm for imputing date/time of onset will be conservative and will classify an adverse event as treatment emergent unless there is definitive information to determine it is pretreatment. Details on classification of adverse events with missing or partial onset dates are provided in [Section 2.5.3](#).

Adverse event incidence tables will present by SOC, HLG, HLT, and PT, sorted in alphabetical order for each treatment group, the number (n) and percentage (%) of patients experiencing an adverse event. Multiple occurrences of the same event in the same patient will be counted only once in the tables within a treatment phase. The denominator for computation of percentages is the safety population within each treatment group. Sorting will be based on results for the dupilumab group.

Analysis of all treatment-emergent adverse events

The following treatment-emergent adverse event summaries will be generated for the safety population.

- Overview of treatment-emergent adverse events, summarizing number (%) of patients with any
 - Treatment-emergent adverse event
 - Serious treatment-emergent adverse event

- Treatment-emergent adverse event leading to death
- Treatment-emergent adverse event leading to permanent treatment discontinuation
- Overview of exposure adjusted incidence rate of treatment-emergent adverse events, summarizing number of patients with an event per 100 patient years with any:
 - Treatment-emergent adverse event
 - Serious treatment-emergent adverse event
 - Treatment-emergent adverse event leading to death
 - Treatment-emergent adverse event leading to permanent treatment discontinuation
- All treatment-emergent adverse events by primary system organ class, showing number (%) of patients with at least 1 treatment-emergent adverse event, sorted by internationally agreed order of primary system organ class
- All treatment-emergent adverse event by primary SOC, HLG, HLT, and PT, showing number (%) of patients with at least 1 treatment-emergent adverse event sorted by the SOC internationally agreed order. The other levels (HLG, HLT, PT) will be presented in alphabetical order
- Number (%) of patients experiencing TEAE(s) presented by PT, sorted by decreasing incidence of PT
- All treatment-emergent adverse events by primary SOC and PT, showing the number (%) of patients with at least 1 treatment-emergent adverse event, sorted by the internationally agreed SOC order and by decreasing incidence of PTs within each SOC.
- Exposure adjusted incidence rate of all treatment-emergent adverse events by primary SOC and PT, showing the number of patients with at least 1 treatment-emergent adverse event per 100 patient-years
- All treatment-emergent adverse events regardless of relationship and related by primary SOC, HLG, HLT and PT, showing the number (%) of patients with at least 1 treatment-emergent adverse event, sorted by the internationally agreed SOC order. The other levels (HLG, HLT, PT) will be presented in alphabetical order
- All treatment-emergent adverse events by maximal severity, presented by primary SOC and PT, showing the number (%) of patients with at least 1 treatment-emergent adverse event by severity (ie, mild, moderate, or severe), sorted by the internationally agreed SOC order and by decreasing incidence of PTs within each SOC
- Number (%) of patients experiencing treatment-emergent adverse event(s) presented by primary and secondary SOC, HLG, HLT, and PT sorted by the internationally agreed SOC order. The other levels (HLG, HLT, PT) will be presented in alphabetical order
- Incidence rate of all common TEAEs (PT $\geq 2\%$) with $\geq 1\%$ higher incidence in one of the groups compared to any other by primary SOC and PT. The relative risk ratio of qualifying TEAEs along its 95% confidence interval will be presented.
- A listing of all treatment-emergent adverse events will be presented

Analysis of all treatment-emergent serious adverse event(s)

- All treatment-emergent serious adverse events by primary SOC, HLG, HLT, and PT, showing the number (%) of patients with at least 1 serious treatment-emergent adverse event, sorted by the internationally agreed SOC order. The other levels (HLG, HLT, PT) will be presented in alphabetical order
- All treatment-emergent serious adverse events regardless of relationship and related to IMP, by primary SOC, HLG, HLT, and PT, showing the number (%) of patients with at least 1 treatment-emergent serious adverse event, sorted by the internationally agreed SOC order. The other levels (HLG, HLT, PT) will be presented in alphabetical order
- All treatment-emergent serious adverse events by primary SOC and PT, showing the number (%) of patients with at least 1 treatment-emergent serious adverse event, sorted by the internationally agreed SOC order and by decreasing incidence of PTs within each SOC
- Exposure adjusted incidence rate of serious treatment-emergent adverse events by primary SOC and PT, showing the number of patients with at least 1 serious treatment-emergent adverse event per 100 patient-years
- A listing of all treatment-emergent serious adverse events will be presented

Analysis of all treatment-emergent adverse event(s) leading to permanent treatment discontinuation or drug interruption

- All treatment-emergent adverse events leading to permanent treatment discontinuation or drug interruption, by primary SOC, HLG, HLT, and PT, showing the number (%) of patients sorted by the internationally agreed SOC order. The other levels (HLG, HLT, PT) will be presented in alphabetical order
- All treatment-emergent adverse events leading to permanent treatment discontinuation or drug interruption, by primary SOC and PT, showing number (%) of patients with at least one TEAE, will be presented by SOC internationally agreed order and by decreasing incidence of PTs within each SOC
- Exposure adjusted incidence rate of treatment-emergent adverse events leading to permanent treatment discontinuation by primary SOC and PT, showing the number of patients with at least 1 treatment-emergent adverse event leading to permanent treatment discontinuation per 100 patient-years

Analysis of adverse events of special interest (AESI) and other selected AE groupings

- All treatment-emergent adverse events, by selected standardized MedDRA query (SMQ) and PT or by laboratory values (as in ALT elevation), showing the number (%) of patients with at least 1 PT, sorted by decreasing incidence of PTs within each SMQ
- For each AESI,
 - Number (%) of patients with any specific treatment emergent AESI
 - Number (%) of patients with any specific serious AESI (regardless of treatment emergent status)
 - Number (%) of patients with any specific treatment emergent serious AESI

- Number (%) of patients with any specific AESI leading to death
- Number (%) of patients with any specific treatment emergent AESI leading to permanent study drug discontinuation
- Number (%) of patients with any specific treatment emergent AESI by maximum intensity, corrective treatment, and final outcome
- Number of specific treatment emergent AESI adjusted by the exposure duration
- Number of patients with any specific treatment emergent AESI adjusted by the exposure duration
- Number of patients with any specific treatment emergent AESI adjusted by the exposure duration at risk. For each AESI, Kaplan-Meier estimates of cumulative incidence at Week 12, 24, 36 and 52 and K-M plot may be provided to depict the course of onset over time if the number of events is large enough
- Number (%) of patients with injection site reactions by the related injection
- Number (%) of patients with different number of injection site reactions

Analysis of pretreatment adverse events

- All pretreatment adverse events by primary SOC and PT, showing the number (%) of patients with at least 1 pretreatment adverse event, sorted by the internationally agreed SOC order and decreasing incidence of PTs within each SOC
- All serious pretreatment adverse events by primary SOC and PT, showing the number (%) of patients with at least 1 pretreatment adverse event, sorted by the internationally agreed SOC order and decreasing incidence of PTs within each SOC
- All pretreatment adverse events leading to permanent treatment discontinuation by primary SOC and PT, showing the number (%) of patients, sorted by the internationally agreed SOC order and decreasing incidence of PTs within each SOC
- All pretreatment adverse events leading to death by primary SOC and PT, showing the number (%) of patients, sorted by the internationally agreed SOC order and decreasing incidence of PTs within each SOC

If only a few patients have pretreatment adverse events leading to permanent treatment discontinuation, a listing will be presented instead of the summary table above.

Subgroup analysis for adverse events

Analysis of adverse events will be performed for below subgroups of interest based on safety population:

- Race (Caucasian/White, Black/of African descent, Asian/Oriental, all the other).
- Sex (Female, Male)
- Ethnicity (Hispanic, Not Hispanic)
- Baseline weight group (≤ 30 , > 30 kg)
- Baseline ICS level (Medium, High)

The subgroup analysis of adverse events includes:

- Overview of treatment emergent AE
- Treatment emergent AE by primary SOC and PT
- Treatment emergent SAE by primary SOC and PT
- Treatment emergent AE leading to permanent treatment discontinuation by primary SOC and PT
- AESI by category

2.4.5.2 Deaths

The following summaries of deaths will be generated for the safety population.

- Number (%) of patients who died by study period (on-study, on-treatment, poststudy)
- Deaths in nonrandomized patients or randomized but not treated patients
- Treatment-emergent adverse events leading to death (death as an outcome on the adverse event case report form page as reported by the Investigator) by primary SOC , HLG, HLT, and PT showing number (%) of patients sorted by internationally agreed SOC order, with HLG, HLT, and PT presented in alphabetical order within each SOC
- All pretreatment adverse events leading to death by primary SOC and PT, showing the number (%) of patients, sorted by the internationally agreed SOC order and decreasing incidence of PTs within each SOC

A listing of deaths will be provided.

2.4.5.3 Analyses of laboratory variables

The analyses of laboratory data will be performed in the safety population. The summary statistics (including number, mean, median, Q1, Q3, standard deviation, minimum and maximum) of all laboratory variables (central laboratory values and changes from baseline) will be calculated for each visit or study assessment (baseline, each postbaseline time point, last on-treatment and/or worst on-treatment value) by treatment group. For each continuous parameters listed in [Section 2.1.4.3](#), mean changes from baseline with the corresponding standard error will be plotted over time in each treatment group. This section will be organized by biological function as specified in [Section 2.1.4.3](#).

The incidence of PCSAs (list provided in [Appendix A](#)) at any time during the treatment-emergent adverse event period will be summarized by biological function and treatment group whatever the baseline level and/or according to the following baseline status categories:

- Normal/missing
- Abnormal according to PCSA criterion or criteria

For parameters for which no PCSA criteria are defined, similar table(s) using the normal range will be provided.

For PCSA analyses, the laboratory measurements obtained at either scheduled or unscheduled visits should be used; and, both the centralized and local test results should be used, as long as their available dates/time is different from each other's. Centralized data will be used preferentially to the local measures in the PCSA analyses when measurements are performed on the same date and at the same time for a given laboratory test.

A listing of PCSAs will be provided.

Drug-induced liver injury

If there is any imbalance in the incidence of liver-related adverse events across the treatment groups, analysis of liver-related adverse events will be performed.

The liver function tests, namely AST, ALT, alkaline phosphatase, and total bilirubin, are used to assess possible drug-induced liver toxicity. The proportion of patients with PCSA values at any postbaseline visit by baseline status will be displayed by treatment group for each parameter. The proportion of patients with PCSA values at any postbaseline visit will also be displayed by duration of exposure for each treatment group.

Time to onset of the initial ALT and AST elevation (>3 x ULN) and total bilirubin elevation (>2 x ULN) (time to first observation of ALT >3 x ULN or total bilirubin >2 x ULN, whichever comes first) will be analyzed using Kaplan-Meier estimates, presented by treatment group. Consideration should be given to the impact of the spacing of scheduled tests. A graph of distribution of peak values of ALT versus peak values of total bilirubin will also be presented. Note that the ALT and total bilirubin values are presented on a logarithmic scale. The graph will be divided into 4 quadrants with a vertical line corresponding to 3 x ULN for ALT and a horizontal line corresponding to 2 x ULN for total bilirubin.

Listing of possible Hy's law cases identified by treatment group (eg, patients with any elevated ALT >3 x ULN, and associated with an increase in bilirubin ≥ 2 x ULN) with ALT, AST, alkaline phosphatase, total bilirubin, and the following complementary parameters: conjugated bilirubin and creatine phosphokinase, serum creatinine, complete blood count, HCV RNA.

Summarize the normalization by parameter (to ≤ 1 x ULN or return to baseline) of elevated liver function tests by categories of elevation (3 x, 5 x, 10 x, 20 x ULN for ALT and AST, 1.5 x ULN for alkaline phosphatase, and 1.5 x and 2 x ULN for total bilirubin), with the following categories of normalization: never normalized, normalized despite treatment continuation of IMP, or normalized after IMP discontinuation. Note that a patient will be counted only under the maximum elevation category.

Change in Blood Eosinophil

Mean and median changes from baseline in eosinophil with the corresponding standard error will be plotted over time in each treatment group for patients with baseline blood eosinophil <0.5 Giga/L and patients with baseline blood eosinophil ≥ 0.5 Giga/L. Number (%) of patients with post-baseline peak blood eosinophil ≥ 1 Giga/L, ≥ 3 Giga/L and ≥ 5 Giga/L will also be summarized in each treatment group and by baseline blood eosinophil status (All, <0.5 Giga/L, ≥ 0.5 Giga/L).

2.4.5.4 Analyses of vital sign variables

The analyses of vital sign data will be performed in the safety population. The summary statistics (including number, mean, median, Q1, Q3, standard deviation, minimum and maximum) of all vital signs variables (values and changes from baseline) will be calculated for each visit or study assessment (baseline, each postbaseline time point, last on-treatment and/or worst on-treatment value) by treatment group. For all parameters, mean changes from baseline with the corresponding standard error will be plotted over time (at same time points) in each treatment group.

The incidence of PCSAs at any time during the treatment-emergent adverse event period will be summarized by treatment group irrespective of the baseline level and/or according to the following baseline status categories:

- Normal/missing
- Abnormal according to PCSA criterion or criteria

2.4.5.5 Analyses of electrocardiogram variables

The analyses of electrocardiogram (ECG) data will be performed in the safety population. The summary statistics (including number, mean, median, Q1, Q3, standard deviation, minimum and maximum) of all ECG variables (values and changes from baseline) will be calculated for each visit or study assessment (baseline, V28 (EOT) and V31(EOS) and ETD, last on-treatment and/or worst on-treatment value) by treatment group.

The incidence of PCSAs at any time during the treatment-emergent adverse event period will be summarized by treatment group irrespective of the baseline level and/or according to the following baseline status categories:

- Normal/missing
- Abnormal according to PCSA criterion or criteria

2.4.6 Analyses of pharmacokinetic, immunogenicity, and pharmacodynamic variables

The PK/ADA analyses will be based on the PK/ADA population as defined in [Section 2.3.3](#).

2.4.6.1.1 Analyses of serum concentrations of SAR231893 (REGN668)

Serum concentrations of SAR231893 (REGN668) will be summarized using arithmetic and geometric means, SD, standard error of the mean (SEM), coefficient of variation (CV), minimum, median and maximum per sampling time by each dose regimen group and overall treatment group. If date and/or time of the drug injection and/or sampling is missing then the concentration will not be taken into account. For drug-treated patients, where concentration values are below the lower limit of quantification (LLOQ), one-half of the LLOQ will be used. Values will be expressed in the tables with no more than three significant figures. For patients in the placebo group,

concentration values are below the LLOQ will be taken into account with a plasma concentration considered equal to 0.

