10.3.4 Handling of Patients After Permanent Treatment Discontinuation

Patients will be followed-up according to the study procedures as specified in this protocol up to the scheduled date of study completion, or up to recovery or stabilization of any AE to be followed-up as specified in this protocol, whichever comes last. Study Investigators should continue background therapy after treatment discontinuation, as guided by their medical judgment.

For patients in Brazil, see [Appendix N](#).

Patients who permanently discontinue the study medication will be asked and encouraged to return to the clinic for study visits and participate in assessments according to the visit schedule until the EOS with a ± 5 day window or up to recovery or stabilization of any AEs. At the time of permanent treatment discontinuation, patients will perform ETD visit with all the assessments defined for the EOT Visit 28. Patients who permanently discontinue early from treatment will not be eligible for the 1-year long-term extension study.

For patients who permanently discontinue the study, under exceptional circumstances where there is no possibility for a patient and parent(s)/caregiver(s)/legal guardian(s) to come to the site for the scheduled follow-up visit, a phone contact may be made after Sponsor's approval is given. During that phone contact, at least information about AEs, concomitant medication and asthma exacerbation events must be collected, and the schedule for these calls should still reflect the visit schedule.

Patients who discontinue early from treatment may be asked to return to the clinic to have additional ADA samples collected for analysis based on the overall assessment of antibody titers and clinical presentation at the time of discontinuation.

All cases of permanent treatment discontinuation should be entered by the Investigator in the e-CRF when considered as confirmed.

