2.3.2 Safety population

The safety population is defined as:

- All patients who actually received at least 1 dose or part of a dose of the IMP, analyzed according to the treatment patients actually received.

In addition:

- Randomized patients for whom it is unclear whether they took the IMP will be included in the safety population as randomized.
- For patients on placebo but accidentally exposed to dupilumab, the treatment group allocation for as-treated analysis will be dupilumab group.
- If a patient is unblinded during the study, all safety data from the patient regardless of before or after unblinding will be included in the safety analyses according to the treatment patients actually received before the unblinding.

All analyses will be provided by treatment regimens as Dupilumab vs placebo. No planned analysis based on the subcategory of dose level will be provided.

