2.3.3 Population for pharmacokinetics, immunogenicity, and pharmacodynamics analyses

The PK population will consist of all patients in the safety population with at least one non-missing serum concentration data. Patients will be analyzed according to the treatment actually received.

The ADA population will consist of all patients in the safety population who had at least one non-missing ADA results (either 'ADA negative' or 'ADA positive') after first dose of the study treatment. Patients will be analyzed according to the treatment actually received.

Biomarkers will be analyzed in the exposed population, consisting of patients in the safety population.

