For the pharmacokinetics, immunogenicity, and pharmacodynamics variables summary, the reference date for the derivation of relative days of measurements will be the date of first IMP administration if the patient is treated with study treatment, or the randomization date if the patient is not treated. Pharmacokinetics /pharmacodynamics variables will be summarized by the analysis window defined in [Table 14](#) for the by visit descriptive analyses. All available values of measurements will be assigned to the appropriate visit window. In the event of multiple

measurements of the same test in the same window, the one closest to the targeted visit date will be used for the by-visit summary. If they are at the same distance to the target day, the latest one will be used. For procedures planned on Visit 2, if it is done on the same date as the first IMP injection but the performance time is missing, it will belong to Visit 2 time window.

Table 14 - Time window for pharmacokinetics/pharmacodynamics variables

Visit	Target day	Time windows for				
		TARC	Exhaled NO	Systemic drug concentration	Anti-drug antibodies	Total IgE/Antigen-specific IgE/IgG 4 panel
Visit 1 (Week -4±1)	-28±7					
Visit 2 (Week 0)	1	1-	1-	1-	1-	1-
Visit 3 (Week 2)	15		1+-21			
Visit 4 (Week 4)	29		22-35			
Visit 5 (Week 6)	43		36-49	1+-63		
Visit 6 (Week 8)	57		50-63			
Visit 7 (Week 10)	71		64-77			
Visit 8 (Week 12)	85	1+-126	78-98	64-126	1+-126	
Visit 10 (Week 16)	113		99-126			
Visit 12 (Week 20)	141		127-154			
Visit 14 (Week 24)	169	127-266	155-182	127-266	127-266	1+-266
Visit 16 (Week 28)	197		183-210			
Visit 18 (Week 32)	225		211-238			
Visit 20 (Week 36)	253		239-266			
Visit 22 (Week 40)	281		267-294			
Visit 24 (Week 44)	309		295-322			
Visit 26 (Week 48)	337		323-350			
Visit 28 (Week 52)	365	267-406	351-378	267-406	267-406	>267
Visit 29 (Week 56)	393		379-406			
Visit 30 (Week 60)	421		407-434			
Visit 31 (Week 64)	449	>406	>434	>406	>406	

1-: up to 1st dose date/time or randomization if patient is not treated; 1+: after 1st dose date/time or randomization date if patient is not treated;

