2.5.5 Unscheduled visits

Unscheduled visit measurements of laboratory data, vital signs, and ECG will not be included in the by-visit summaries, but will be used for computation of baseline, worst value and PCSAs.

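### With no treatment-status condition on the by-visit concentration summary, samples from children who have stopped dupilumab pull down the Week 24 and Week 52 means

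*SAP*

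**What the plan says.** SAP 2.1.5 schedules predose samples at Weeks 0, 6, 12, 24, 52 and 64. Under SAP 2.4.6.1.1 the concentrations are "summarized using arithmetic and geometric means, SD, standard error of the mean (SEM), coefficient of variation (CV), minimum, median and maximum per sampling time", by dose regimen and overall. The only exclusion there concerns timing records: "If date and/or time of the drug injection and/or sampling is missing then the concentration will not be taken into account". Low values in children who received dupilumab are substituted and not dropped; the rule is that "where concentration values are below the lower limit of quantification (LLOQ), one-half of the LLOQ will be used".

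The population carries no on-treatment condition: "The PK population will consist of all patients in the safety population with at least one non-missing serum concentration data" (SAP 2.3.3).

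SAP 2.5.4 says of PK variables: "All available values of measurements will be assigned to the appropriate visit window". In Table 14 the drug-concentration windows run from after the first dose to Day 63 (Week 6), then Days 64-126 (Week 12), 127-266 (Week 24), 267-406 (Week 52) and beyond Day 406 (Week 64). One value is kept per window, the one closest to the target day.

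Protocol 10.3.4 asks children who permanently stop the study drug to "return to the clinic for study visits and participate in assessments according to the visit schedule until the EOS". Appendix N makes follow-up to end of study mandatory for Brazilian children taken off drug because of the yellow fever outbreak.

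SAP 2.5.4 does contain a treatment-epoch restriction, but only for the on-treatment efficacy analyses.

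**The concern.** Systemic exposure is a secondary objective (Protocol 5.2, SAP 1.2.2). Protocol 4.2 chose the regimen to match effective adult exposure, which it describes through mean steady-state troughs of 28.3 and 58.5 mg/L for the two adult q2w regimens. A reader will set the children's by-visit means beside figures of that kind.

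If the Week 24 and Week 52 means mix on-treatment troughs with samples taken weeks or months after the last injection, they no longer describe exposure on the regimen. Because discontinuation accumulates, the means would drift down over the year even if on-treatment exposure were constant. That could be read as under-dosing or as falling exposure. The same samples can enter the concentration-by-visit plots by ADA class (SAP 2.4.6.1.2), where stopping drug could be mistaken for an effect of antibodies.

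**Working it through.** **The rules applied to one child.** Suppose a child stops drug and has the early-discontinuation visit on Day 300. That visit carries the Week 52 assessments, including a drug-concentration sample. If the child also attends Week 52 (Day 365), both samples fall in the Day 267-406 window. Their distances from target are 65 days and 0 days, so the later, off-drug sample is kept.

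**The plan's own figure.** Linear discontinuation of 20% at one year gives mean exposure 1 - 0.20/2 = 0.90 year, as stated. On the same line, the share discontinued is 0.20 x 12/52 = 4.6% at Week 12, 0.20 x 24/52 = 9.2% at Week 24 and 20% at Week 52 (0.20 x 268 = 53.6 dupilumab children). The documents do not say how many of these would still be sampled.

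**Size with washed-out samples.** Let a share f of samples sit at LLOQ/2 and the rest at trough C. Then:

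- geometric-mean ratio = ((LLOQ/2)/C)^f
- arithmetic-mean ratio = approximately 1 - f

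C is taken as 28.3 or 58.5 mg/L, the adult values in Protocol 4.2 used as a proxy. LLOQ/2 = 0.025 to 0.25 mg/L and f = 5 to 10% are assumptions.

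| C (mg/L) | LLOQ/2 (mg/L) | f = 5% | f = 10% |
|---|---|---|---|
| 28.3 | 0.25 | 0.79 | 0.62 |
| 58.5 | 0.25 | 0.76 | 0.58 |
| 28.3 | 0.025 | 0.70 | 0.50 |
| 58.5 | 0.025 | 0.68 | 0.46 |

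The geometric mean is therefore 21 to 54% too low, and the arithmetic mean about 5 to 10% too low.

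**Gradual washout, by visit.** Take stopping times as uniform on the 20% line, and let a share r of stopped children still be sampled. Concentration falls log-linearly from C to LLOQ/2 over 12 weeks, starting about two weeks after the last dose. It therefore ends near last dose + 98 days, the end of the residual treatment epoch, used here as an assumed washout time. At week w, with d = 0.20 x w/52, the off-drug share of samples is s = rd/(1 - d + rd). The average fraction of the log-fall completed is 1 - 6/w for w of 12 or more. The ratio is ((LLOQ/2)/C)^(s(1 - 6/w)). For LLOQ between 0.05 and 1 mg/L and both values of C:

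| Sampled share r | Week 12 | Week 24 | Week 52 |
|---|---|---|---|
| 25% | 0.96-0.98 | 0.87-0.93 | 0.67-0.81 |
| 50% | 0.91-0.95 | 0.76-0.86 | 0.47-0.67 |
| 100% | 0.84-0.91 | 0.58-0.76 | 0.25-0.49 |

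Example (r = 50%, Week 52, C = 28.3, LLOQ/2 = 0.025): s = 0.10/0.90 = 0.111, the exponent is 0.111 x 0.885 = 0.098, and the ratio is 0.50.

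**What the half-LLOQ rule contributes.** Substituting LLOQ instead multiplies the ratio by 2^f, which is 1.07 at f = 10%: 0.46 becomes 0.49. The substitution value is secondary to the presence of the samples.

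**The median.** With f of the values at the bottom, the reported median is the (0.5 - f)/(1 - f) quantile of the on-treatment values: 0.45/0.95 = 47th percentile at f = 5%, 0.40/0.90 = 44th at f = 10%.

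**The case against.** The strongest reply is that the size is not a finding about this trial. The documents give no LLOQ. The 20% belongs to the sample-size calculation for an endpoint that keeps off-treatment follow-up, so it may describe loss to follow-up, and children lost to follow-up give no sample. This stands: the figures above are conditional.

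Second, the PK variable is already defined as predose samples at named visits, records with missing times are dropped, and one value is kept per window. All true, so it would be wrong to say that every sample collected is averaged. None of these rules removes a scheduled sample from a child who has stopped drug.

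Third, the table is descriptive. It also reports the median, minimum and CV, and a minimum at LLOQ/2 would be a visible sign. Protocol 11.4.4.1 allows population PK modelling, which can use actual dosing histories, but only if warranted and in a separate document. These points limit the consequence. They do not make the planned means right.

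A reader might also make much of two other routes. Unscheduled samples taken for an SAE or AESI can enter a PK window, because the relevant exclusion reads "Unscheduled visit measurements of laboratory data, vital signs, and ECG will not be included in the by-visit summaries" and does not name drug concentrations. And "For patients on placebo but accidentally exposed to dupilumab, the treatment group allocation for as-treated analysis will be dupilumab group" (SAP 2.3.2). Both follow from the text, but no frequency is given for either, and SAE/AESI samples are recorded on their own form. They are minor beside discontinuation.

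**Conclusion.** The point holds as a gap in the analysis rules. As written, the SAP admits off-drug samples into the Week 24 and Week 52 concentration means and biases them downward. Week 12 is little affected, and Week 64 is off drug by design. The cause is the missing treatment-status condition in SAP 2.4.6.1.1, 2.3.3 and 2.5.4; half-LLOQ substitution only magnifies it on the geometric scale.

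Under the stated assumptions (LLOQ/2 of 0.025 to 0.25 mg/L, troughs of 28.3 to 58.5 mg/L, 5 to 10% of samples washed out), the geometric mean is about 21 to 54% too low and the arithmetic mean about 5 to 10% too low.

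A reader might infer that the geometric mean is cut by up to half. The documents do not support that as a bound: with every stopped child sampled the Week 52 cut could exceed half, and with few sampled it is well below. Nor do they support reading the 20% as the share off drug but sampled, or any consequence for an efficacy test. The point is worth correcting before the tables are produced, but it does not threaten the trial's main conclusions.

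**What to change.** In SAP 2.4.6.1.1:

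- Base the Week 6 to Week 52 by-visit summary on scheduled predose samples from children who have not permanently discontinued the study drug at the time of sampling.
- Allow the visit window after the last planned dose. The treatment epoch ends at last dose + 14 days, so a strict epoch filter would drop valid Week 52 samples taken up to 3 days later (Days 15 to 17 after the Week 50 dose).
- Keep children who missed doses but remain on treatment. Their low values are real exposure, and a strict time-since-dose filter would select adherent children and bias the means upward.
- Keep the as-treated PK population of Protocol 11.3.3 and SAP 2.3.3.
- Exclude unscheduled SAE/AESI samples from the by-visit windows.
- List or plot off-treatment samples by days since last dose.
- State the LLOQ and report the number of values below it at each visit.

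The cost is a few lines of text and slightly fewer samples per visit. SAP 2.4.6.1.1 already needs injection and sampling times, and no data are lost because the excluded samples are still shown.
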